Endoscopic Retrograde Cholangiopancreatography (ERCP) is an important method for diagnosing and treating biliary and pancreatic diseases, among which common bile duct stones are one of the most frequently encountered causes. However, ERCP is an invasive procedure with a high risk of complications, including acute pancreatitis, bleeding, hollow organ perforation, and infection. Among these, infectious complications occur in approximately 5% to 18% of cases and account for around 10% of ERCP-related mortality¹⁻³.

To minimize the risk of infection, several strategies have been proposed, such as limiting the injection of contrast into the bile duct, aspirating bile to reduce biliary pressure, ensuring complete biliary drainage, and using prophylactic antibiotics⁴. However, the clinical effectiveness of prophylactic antibiotic use remains controversial. A meta-analysis by Cochrane et al. (2010) showed that prophylactic antibiotics can reduce the risk of bacteremia and cholangitis⁵. In contrast, a more recent meta-analysis by Maria Fernanda Shinin Merchan (2022), along with several other studies, suggested that prophylactic antibiotics may reduce

the rate of bacteremia but do not significantly decrease the incidence of cholangitis, sepsis, post-ERCP pancreatitis, or mortality⁶⁻⁸.

Rational antibiotic use remains a significant challenge for clinicians, as broad-spectrum antibiotic treatment can lead to unnecessary costs and contribute to the growing problem of antibiotic resistance—a serious global health concern causing approximately 700,000 deaths annually and an estimated economic burden ranging from 1 to 3.4 trillion USD. This figure continues to rise⁹⁻¹¹.

According to guidelines from major organizations such as the American Society for Gastrointestinal Endoscopy (ASGE) and the European Society of Gastrointestinal Endoscopy (ESGE), routine prophylactic antibiotic use is not recommended, except in cases of incomplete biliary drainage or in immunocompromised patients. However, these recommendations are based on low-quality evidence and remain weak in strength.

Therefore, we designed this study to evaluate whether prophylactic antibiotic use can reduce infectious complications after ERCP in patients with common bile duct stones.

4. Objectives

To evaluate whether prophylactic antibiotic use can reduce infectious complications after ERCP in patients with common bile duct stones.

5. Study Design

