Interventional Study, open-label, randomized controlled trial.

6. Methodology

- Eligibility

Participant inclusion criteria:

- Patients ≥ 18 years with common bile duct stones are diagnosed by abdominal ultrasound, endoscopic ultrasound, CT scan, or abdominal MRI.
 - No signs of cholangitis at the time of admission, defined by the following criteria:
 - + Non fever (temperature $< 37^{\circ}$ C)
 - + White blood cell count between 4 G/L and 10 G/L
 - Good general condition, classified as ASA Physical Status I or II

Participant exclusion criteria:

• Patients with severe coagulopathy (INR > 1.5 or platelet count < 50 G/L)

Patients with severe systemic illnesses, such as unstable myocardial infarction, respiratory failure, or circulatory failure

- Patients with duodenal perforation or failed ERCP due to inability to access the papilla
- Patients with active infections in other organ systems requiring antibiotic therapy
- Patients have received any systemic antibiotics within 48 hours prior to the ERCP procedure
 - Patients are allergic to antibiotics used in the study.

- Interventions

Patients with common bile duct stones without signs of cholangitis at the time of hospital admission. Patients have an indication for ERCP stone extraction and randomly assigned to one of three study groups by using a simple randomization method in which the remainder of their record number divided by 3 determined the group allocation.

- •Control Group: No Antibiotics Group (Group 1)
- + Medication: normal saline
- + Administration: No antibiotics administered. Patients will receive an intravenous infusion of normal saline on the day of the procedure.
 - •Prophylactic Antibiotic Group (Group 2)
 - + Medication: Amikacin
- + Administration: Amikacin at a dose of 15 mg/kg, diluted in 0.9% NaCl to a total volume of 100mL, administered via intravenous infusion over 60 minutes

+ Timing: Administered 60 minutes before ERCP procedure. For patients with renal impairment,

the Amikacin dose will be adjusted based on glomerular filtration rate (GFR).

- + Other Names: Antibiotic prophylaxis
- •Full-dose Antibiotic Group (Group 3)
- + Medication: Amikacin + Third-generation Cephalosporine
- + Administration: Amikacin at 15 mg/kg/day in combination with Cefoperazone 2 g twice daily, administered by slow intravenous injection every 12 hours
- + Timing: From before the ERCP procedure until hospital discharge, typically lasting 4–7 days.

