After undergoing ERCP, patients will be monitored for signs of infectious complications through clinical symptoms and laboratory tests within 24 to 48 hours post-procedure.

Clinical symptoms include: pulse, blood pressure, consciousness, abdominal pain, fever, jaundice, and melena.

Laboratory tests include: complete blood count and blood biochemistry (urea, creatinine, GOT, GPT, GGT, ALP, total bilirubin, direct bilirubin, CRP, procalcitonin, amylase, lipase).

Patients with high fever > 38°C will undergo blood culture and abdominal CT scan if necessary.

Patients with complications will be monitored clinically, undergo laboratory tests, and receive treatment according to guidelines until they are stable and discharged from the hospital.

[figure not shown]
Outcomes

• Primary Outcome:

Infectious Complications post-ERCP: Fever > 38°C occurring within 24 to 48 hours following ERCP. ¹²

- Secondary Outcomes:
- + Cholangitis: worsening right upper quadrant abdominal pain; fever (ear temperature >38.0 °C); evidence of systemic inflammation: either elevated white blood cell count (>10 G/L) or increased C-reactive protein levels (>10 mg/L), or a further rise if already above the upper normal limit (UNL) prior to ERCP; and indicators of hepatobiliary dysfunction—such as jaundice (total bilirubin >2.0 mg/dL, or worsened if pre-existing), or elevated liver enzymes (GGT, ALP, AST, ALT >1.5×UNL, or further increased if already above UNL before the procedure)¹³.
- + Cholecystitis: Diagnosis was made according to the criteria of the Tokyo Guidelines 2018(TG18)¹³.
 - + Inflamatory markers: WBC, CRP, Procalcitonin
 - + Bacteremia: Positive blood culture for bacteria¹⁴
 - Other Outcomes:
- + Bleeding: Bleeding observed during the procedure or clinical signs such as melena, anemia, and a decrease in hemoglobin level exceeding 2 g/dL^{15} .
 - + Pancreatitis: Diagnosis based on the Revised Atlanta Classification (2012)¹⁶

- Study flowchart

3. Safety considerations

Patients who show signs of infection after undergoing ERCP will be treated with antibiotics according to the Tokyo Guidelines 2018 and the recommendations of the Vietnamese Ministry of Health until they are stable and discharged from the hospital.

Patients who develop other complications such as acute pancreatitis or gastrointestinal bleeding will be treated according to the respective protocols for acute pancreatitis and gastrointestinal bleeding until they are stable and discharged.

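### Open-label trial with no masked outcome assessment, and a control saline infusion that neither matches Group 2's infusion nor masks anyone

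*Protocol*

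**What the plan says.** Study Design: "Interventional Study, open-label, randomized controlled trial". No masking of patients, care staff or outcome assessors is described anywhere in the protocol.

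The aim, given in the Project Summary and Rationale and repeated under Objectives, is "to evaluate whether prophylactic antibiotic use can reduce infectious complications after ERCP in patients with common bile duct stones". The contrast that answers it most directly is Group 2 (prophylaxis) against Group 1 (no antibiotics).

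Methodology, Interventions, describes the arms as follows:
- Group 1: "Patients will receive an intravenous infusion of normal saline on the day of the procedure".
- Group 2: amikacin "diluted in 0.9% NaCl to a total volume of 100mL, administered via intravenous infusion over 60 minutes", with timing "Administered 60 minutes before ERCP procedure".
- Group 3: amikacin plus cefoperazone, "From before the ERCP procedure until hospital discharge, typically lasting 4–7 days".
- Allocation: "the remainder of their record number divided by 3 determined the group allocation".

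Under Outcomes, the primary outcome is a temperature above 38°C between 24 and 48 hours after ERCP. Cholangitis, a secondary outcome, has "worsening right upper quadrant abdominal pain" among its criteria. Blood culture and CT follow high fever, with CT left to need. No temperature measurement schedule is stated.

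**The concern.** The control arm receives an intravenous infusion, but the infusion is specified too loosely to resemble Group 2's, and in an open-label trial it conceals nothing. Patients and staff know the arm when temperature is taken, when pain is reported, when CT is considered, and when cholangitis, cholecystitis, pancreatitis and bleeding are classified. Staff who expect more infection in untreated patients may look harder for it there, which would make antibiotics appear more effective. With 36 patients per arm and few expected events, a small difference in how events are found or labelled would visibly move the estimate.

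**Working it through.** **1. The two infusions side by side**

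| Feature | Group 1 | Group 2 |
|---|---|---|
| Fluid | normal saline | amikacin in 0.9% NaCl |
| Volume | not stated | 100 mL |
| Duration | not stated | 60 minutes |
| Timing | day of the procedure | 60 minutes before ERCP |

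As written, the Group 1 infusion is not a match for Group 2's.

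**2. Could matching alone mask the comparison?** No. The arm is the remainder of the record number divided by 3, so anyone who sees the record number can work it out. Concealed allocation is a precondition. Group 3, with repeated dosing until discharge, stays recognisable in any case.

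**3. The plan's own sample size.** Inputs from Sample Size Calculation: α = 0.05, power 0.80, w = 0.3, 2 degrees of freedom. The noncentrality is N × w² = 108 × 0.09 = 9.72. The noncentral chi-square distribution gives power 0.804 at N = 108, the smallest N that reaches 0.80. The stated figure reproduces. Masking changes none of these inputs, so N stays at 108 (36 per arm).

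**4. How much one patient counts.** 1/36 = 2.8 percentage points. At the 5% to 18% infection rate in the Rationale, 36 patients yield 36 × 0.05 = 1.8 to 36 × 0.18 = 6.5 expected events.

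**5. Illustration of differential capture (assumption; the documents give no basis for these inputs).** Suppose the true rates are equal, controls have 90% or 95% of events captured, and Group 2 has 70% or 80%. The expected relative risk is Group 2 capture divided by control capture:

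| | Control 90% | Control 95% |
|---|---|---|
| Group 2 70% | 0.70/0.90 = 0.78 | 0.70/0.95 = 0.74 |
| Group 2 80% | 0.80/0.90 = 0.89 | 0.80/0.95 = 0.84 |

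The range over all four combinations is 0.74 to 0.89.

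In patients, at a true rate of 18%, the expected gap in recorded events runs from 36 × 0.18 × (0.90 − 0.80) = 0.65 to 36 × 0.18 × (0.95 − 0.70) = 1.62. At 5% it runs from 36 × 0.05 × 0.10 = 0.18 to 36 × 0.05 × 0.25 = 0.45. A shift of this size in the relative risk thus corresponds to fewer than two patients.

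**6. Effect on significance.** At a true rate of 18%, the two-proportion normal approximation (n = 36 per arm, two-sided 0.05) gives a chance of about 4% to 8% of a nominally significant result favouring Group 2, against 2.5% without bias. The main effect is on the estimate.

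**The case against.** The strongest reply is that open-label is a declared design choice. The control arm is labelled as receiving no antibiotics, and the saline is never called a placebo. That stands: the protocol does not contradict itself here, and a reader should not infer a placebo control that failed.

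The primary outcome is also a numeric threshold. Cholangitis, as written, joins pain to fever, a systemic inflammation criterion and a hepatobiliary criterion, so a pain report alone cannot create a case. Laboratory and symptom monitoring is described for patients generally. This stands too and lowers the exposure. It does not remove it, because no temperature schedule is fixed: an arm checked more often has more chances to cross the threshold.

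A reader might infer that masking would cost almost nothing because saline is already being hung. The documents do not support that. It would need a new concealed allocation list and someone outside care and assessment to prepare weight- and GFR-adjusted infusions, and the protocol names no such person. Even then, the planned three-group test would combine two masked arms with one open arm.

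Timing counts as well. The study window opens in December 2022 and the reference list includes a January 2024 paper, so enrolment may already have begun. Masking introduced part-way would create masked and unmasked cohorts. This weighs against matched bags as the first remedy, but not against masked classification, which can still be done for patients already treated.

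Finally, the direction of bias is not proven. Prompter treatment of suspected infection in controls could suppress later fever and push the other way.

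**Conclusion.** The point holds in a limited form. The objective's comparison is unmasked, no masked outcome assessment is described, and the control infusion is too loosely specified to match Group 2's. The judgement-based outcomes are the most exposed. Fever above 38°C is exposed mainly through how often temperature is measured. Bias favouring antibiotics is likely but not certain.

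The documents give no figure for its size. The relative risk range of 0.74 to 0.89 rests wholly on the assumed capture rates, equal true rates and no drug effect. It shows how sensitive a trial with about 2 to 6 events per arm would be, and it is not an estimate of the bias in this trial. A reader might go further and call the primary result invalid. Nothing in the documents supports that.

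**What to change.** 1. **Masked classification and a common temperature schedule.** Have existing study staff classify every outcome against the protocol's definitions, using CRF data that carry only the study ID, with treatment fields and the record number removed, before the group code is merged into the dataset. The study ID already exists, and the step works even if enrolment has begun. It protects classification but cannot correct data collected by staff who know the arm, so the protocol should also state one temperature schedule that applies to all three arms. Cost: some extra data handling and an ordered merge, with no extra patients.

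2. **Matched infusion, only together with concealed allocation.** State the control saline's volume, rate and timing so that they match whatever Group 2's infusion has. To mask Group 1 against Group 2, also replace the record-number rule with a concealed list, and have coded bags prepared away from care and assessment staff. Group 3 stays open. Cost: a new allocation list, off-ward preparation and a code-break procedure. If recruitment is under way, patients enrolled before and after the change must be distinguishable in the analysis.

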Patients who experience duodenal perforation during ERCP will be withdrawn from the study and treated with endoscopic clip placement or surgery.

Patients who are admitted while awaiting ERCP and develop signs of infection with a fever >37°C will be withdrawn from the study and treated with antibiotics according to the Tokyo Guidelines 2018 and the recommendations of the Vietnamese Ministry of Health

4. Follow-up

Participants will be followed for 7 days after the ERCP procedure to monitor for adverse events, including post-ERCP pancreatitis, cholangitis, bleeding, or gastrointestinal perforation. Monitoring will be performed through daily clinical assessments during hospitalization, supported by laboratory tests (Ure, Creatinin, GOT, GPT, GGT, ALP, total bilirubin, direct bilirubin, CRP, procalcitonin, amylase, lipase and CT scan as needed) and vital signs.

For participants discharged before day 7, follow-up will continue via telephone to assess health status and identify any signs or symptoms suggestive of post-procedural complications. If concerning symptoms are reported, participants will be advised to return for medical evaluation.

All adverse events (AEs) and serious adverse events (SAEs) will be documented, managed appropriately, and reported in accordance with the study's safety protocol. Follow-up will conclude at day 7 post-ERCP unless complications arise, in which case follow-up will continue until resolution.

5. Data management and statistical analysis

- Data Management:

Study data will be collected using paper-based Case Report Forms (CRFs) and subsequently entered manually into a Microsoft Excel spreadsheet designed by the research team. Each participant will be assigned a unique study identification number (ID) to maintain confidentiality. The dataset will be encrypted and stored on a password-protected computer with access restricted to authorized study personnel.

- Statistical analysis

Data analysis will be performed using SPSS version 22.

• Descriptive analysis

Quantitative variables will be presented as mean and standard deviation if normally distributed, or as median and interquartile range if not normally distributed.

Qualitative variables (e.g., gender, rate of cholangitis, etc.) will be presented as frequency and percentage.

• Comparison between groups

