Categorical variables (e.g., rate of cholangitis, mortality rate, etc.) will be compared among the three groups using the Chi-square test. If expected cell counts are small, Fisher's exact test will be used.

Continuous variables (e.g., length of hospital stay, biochemical indices, etc.) will be compared using one-way ANOVA if the data are normally distributed, or the Kruskal-Wallis test if not.

If statistically significant differences are found among the three groups, post-hoc analyses will be conducted to determine which group pairs differ. Differences between groups will be assessed using Relative Risk (RR) along with a 95% Confidence Interval (95% CI). A p-value of less than 0.05 will be considered statistically significant.

• Sample Size Calculation

The sample size was calculated using G*Power software (version 3.1), applying a Chisquare test (goodness-of-fit test) with the following parameters: significance level (α) = 0.05, power (1 – β) = 0.80, and a medium effect size (w = 0.3) as recommended by Cohen¹⁷. This yields a total sample size of 108 participants (36 per group) for a chi-square goodness-of-fit test with 2 degrees of freedom.

6. Quality assurance

The study will be conducted in accordance with ethical regulations for biomedical research involving human participants and has been approved by the Institutional Ethics Committee.

To ensure quality and consistency throughout the implementation process, the research team has developed standard procedures for all steps, including patient selection, intervention, data collection, and data processing.

Monitoring of adverse events, as well as ensuring the integrity and safety of participants, will be jointly conducted by the research team members, the principal investigator, and the hospital's Ethics Committee.

7. Expected outcomes of the study

The study is expected to provide scientific evidence on the effectiveness of prophylactic antibiotic use in preventing post-ERCP infections in patients with common bile duct stones. This may contribute to improving clinical practice guidelines, optimizing antibiotic use, and reducing the risk of antibiotic overuse and resistance

8. Dissemination of results and publication policy

Results will be submitted to peer-reviewed journals and presented at scientific meetings. Participants will be informed of the study outcomes upon request

9. Duration of the Project

The study is expected to be conducted from December 2022 to December 2025

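### The written GFR adjustment of amikacin stands only under the single-dose arm (Group 2); the repeat-dose arm (Group 3) should be covered by the same rule

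*Protocol*

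**What the plan says.** The dosing rules are in the Interventions part of section 6, Methodology, where each arm has its own bullets.

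- **Group 2 (prophylactic).** One amikacin infusion of 15 mg/kg before ERCP. The Timing bullet goes on to say that, for renally impaired patients, "the Amikacin dose will be adjusted based on glomerular filtration rate (GFR". Group 2's Other Names bullet follows, and only then does Group 3 begin.
- **Group 3 (full dose).** The Administration bullet reads "Amikacin at 15 mg/kg/day in combination with Cefoperazone 2 g twice daily, administered by slow intravenous injection every 12 hours", and the Timing bullet reads "From before the ERCP procedure until hospital discharge, typically lasting 4–7 days". Neither mentions renal function or refers to Group 2.

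Three other places bear on the point:

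- **Eligibility.** Patients must be in "Good general condition, classified as ASA Physical Status I or II". Severe systemic illness is excluded, with cardiac, respiratory and circulatory examples. There is no creatinine or GFR limit.
- **Laboratory tests.** Creatinine is in the panel for the first 24 to 48 hours after ERCP (Interventions). It appears again under Follow-up, which provides for "daily clinical assessments during hospitalization, supported by laboratory tests (Ure, Creatinin" and further tests.
- **Quality assurance.** The protocol states that "the research team has developed standard procedures for all steps, including patient selection, intervention, data collection, and data processing". Those procedures are not part of the document.

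**The concern.** By writing a GFR rule, the protocol accepts that renally impaired patients may enrol and that their amikacin dose should then change. Nothing in eligibility removes them. Yet the rule appears where amikacin is given once and is missing where it is given daily for several days.

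Someone preparing doses from the Group 3 bullets alone would find a fixed daily dose with no renal exception. What is at stake is the safety of the few such patients allocated to Group 3. Study-drug dosing is protocol content, so this is not something left to a statistical analysis plan.

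**Working it through.** **Inputs, all from Interventions.** Group 2: 15 mg/kg, one administration. Group 3: 15 mg/kg/day for a typical 4 to 7 days. The protocol states no cumulative dose, so there is no figure of its own to reproduce here.

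**Exposure per patient**

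Cumulative dose = daily dose × number of days.

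| Arm | Calculation | Total |
|---|---|---|
| Group 2 | 15 × 1 | 15 mg/kg |
| Group 3, 4 days | 15 × 4 | 60 mg/kg |
| Group 3, 7 days | 15 × 7 | 105 mg/kg |

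The ratio to Group 2 is 60/15 = 4 to 105/15 = 7. This assumes one full, unadjusted daily dose on each day of the typical stay; a shorter or longer stay moves the total in proportion. The 12-hourly wording in Group 3 may govern cefoperazone alone or both drugs, but the amikacin total is fixed per day either way.

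**Coverage of the written rule**

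| Item | Group 2 | Group 3 |
|---|---|---|
| Amikacin dose stated | yes | yes, restated |
| GFR adjustment in the arm's own bullets | yes | no |
| Reference to the other arm's rule | not needed | none |
| Creatinine listed before the first dose | no | no |
| Creatinine listed after ERCP | yes | yes |
| Creatinine result linked to a later dose | not applicable, one dose | no |

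Both lists containing creatinine concern the time after ERCP, while the first amikacin dose in either arm comes before it. The Group 2 rule therefore implies a pre-dose creatinine that the protocol does not list. In Group 3 the later results could guide repeat doses, but no sentence says that they do.

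**What cannot be computed.** The protocol gives neither the share of renally impaired patients nor the size of the GFR adjustment. A number of patients affected, an excess dose or a risk of harm would each rest on invented inputs, so none is given.

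**Sample size.** The planned total of 108 reproduces: with w = 0.3, 2 degrees of freedom and alpha 0.05, the noncentrality is 108 × 0.09 = 9.72 and the power is 0.804. The dosing wording does not enter that calculation.

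**The case against.** The strongest objection is that the sentence names no arm. It speaks of patients with renal impairment and of the amikacin dose in general, so its restriction to Group 2 comes from layout alone. The protocol may simply give amikacin details at first mention; the dilution, for instance, is described only under Group 2. This stands as far as intent goes: the rule may well have been meant for both arms. It does not make the text clear, because Group 3 restates the amikacin dose instead of referring back.

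Second, documents that are not shown may contain the rule. The standard procedures are said to cover the intervention, and Follow-up mentions a separate safety protocol in connection with adverse event reporting. The study flowchart is also missing from the text at hand. This stands too, and it is why citing an existing procedure would be enough.

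Third, the risk is small and watched. Patients are ASA I or II, creatinine is measured after ERCP, and "All adverse events (AEs) and serious adverse events (SAEs) will be documented, managed appropriately, and reported". These points keep the matter minor. They do not replace a dosing rule, since measuring creatinine does not say what to do with the result.

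A reader might infer more: that Group 3 patients would in practice be overdosed, or that the arms are handled so differently that the comparison is biased. The documents support neither. The first presumes that clinicians would adjust amikacin in one arm and ignore renal function in the other, which nothing in the text says. The second would need evidence that the wording changes the fever outcome or the analysis, and there is none.

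**Conclusion.** The point holds as a minor patient-safety correction to the written dosing rule. The visible text puts the GFR adjustment only under the arm receiving 15 mg/kg once. It omits the adjustment from the arm receiving 60 to 105 mg/kg over a typical stay, four to seven times as much, and no eligibility criterion names renal impairment.

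Confidence is high that the wording is absent from Group 3. Whether practice would depart from the rule is unknown, because the intended scope of the sentence and the content of the standard procedures are not visible. The exposure range rests on the protocol's typical duration and on full daily dosing. No effect on the between-arm comparison, power or sample size is claimed.

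**What to change.** State the rule once for both amikacin arms, for example: *In Groups 2 and 3 the amikacin dose is adjusted to GFR, calculated from a creatinine available before the first dose. In Group 3, repeat doses are checked against the creatinine measured during the hospital stay.* If a standard procedure already says this, cite it in the Group 3 bullets instead.

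The cost is one short amendment and the naming of a pre-dose creatinine, which the Group 2 rule already implies. It could probably be run on blood taken anyway, since eligibility requires a white cell count and the cholangitis definition compares results with pre-ERCP values. The Group 3 check uses results already collected. No extra patients are needed, and no endpoint or analysis changes.

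### Patients are removed for perforation, failed ERCP or fever while waiting, events that arise after dosing or after the eligibility check, so the arms can lose patients unequally and bias can enter

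*Protocol*

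**What the plan says.** Three rules in the protocol take patients out.

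- **Section 6, exclusion criteria.** One criterion reads "Patients with duodenal perforation or failed ERCP due to inability to access the papilla".
- **Safety considerations, perforation.** "Patients who experience duodenal perforation during ERCP will be withdrawn from the study".
- **Safety considerations, waiting period.** "Patients who are admitted while awaiting ERCP and develop signs of infection with a fever >37°C will be withdrawn from the study".

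The setting in which they operate:

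- Eligibility is tied to an earlier moment: "No signs of cholangitis at the time of admission".
- The group follows from the record number: "the remainder of their record number divided by 3 determined the group allocation". The time of allocation is not given in the text.
- The design is described as "Interventional Study, open-label, randomized controlled trial".
- Group 1 receives saline on the day of ERCP and Group 2 is dosed 60 minutes before it. Group 3 starts before ERCP with no fixed lead time.
- The Follow-up section keeps participants for 7 days "to monitor for adverse events, including post-ERCP pancreatitis, cholangitis, bleeding, or gastrointestinal perforation".
- A further exclusion reads "Patients have received any systemic antibiotics within 48 hours prior to the ERCP procedure", without limiting it to non-study antibiotics.

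The protocol text does not say whether removed patients are replaced or how they count in the comparison. The sample size paragraph has no allowance for them.

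**The concern.** Eligibility is anchored to the ERCP rather than to allocation. Perforation and failed access to the papilla are results of the procedure. By the time either is known, Group 2 has had its infusion and Group 3 has started antibiotics. Listing them as exclusion criteria means dropping treated patients after the fact.

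Fever during the wait is a different case. It arises after the admission check, and the word withdrawn suggests that the patient was already in the study. In Groups 1 and 2 it will mostly come before any study infusion. In Group 3 it can come after antibiotics have begun, and those antibiotics could suppress it. The same incipient infection might then remove a patient from Group 1 or 2 and leave a comparable patient in Group 3. Staff can also know the arm when they decide whether a patient shows signs of infection.

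At stake is whether the groups compared are the groups allocated. A patient withdrawn from the study may have no recorded outcome, and an analysis plan cannot recover data that were never collected. The arm-by-arm account of perforation is also put in doubt, because one section withdraws these patients and the next lists perforation among the events to be followed.

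**Working it through.** **1. The plan's own figure.** Inputs from the sample size paragraph: alpha 0.05, power 0.80, w = 0.3, 2 degrees of freedom. Power is the probability that a noncentral chi-square with 2 df and noncentrality N × w² exceeds the 5% critical value, 5.991. At N = 108 the noncentrality is 108 × 0.09 = 9.72 and the power is 0.804. At N = 107 it is 0.7998. The stated 108 is reproduced, with nothing added for removals.

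**2. Loss of numbers.** The shares removed are assumed, since the protocol gives none, and removed patients are taken as not replaced.

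| Removed | N left | N × 0.09 | Power |
|---|---|---|---|
| 0% | 108 | 9.72 | 0.804 |
| 5% | 102.6 | 9.23 | 0.782 |
| 10% | 97.2 | 8.75 | 0.758 |
| 15% | 91.8 | 8.26 | 0.732 |

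To finish with 108 analysed, 108/0.95, 108/0.90 or 108/0.85 would have to be allocated: 114, 120 or 128.

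**3. Weight of a single patient.** The protocol's background rate is 5% to 18%. Per arm this gives 36 × 0.05 = 1.8 to 36 × 0.18 = 6.5 events. One patient is 1/36 = 2.8 percentage points.

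**4. Sensitivity of the test.** Assume 6, 2 and 2 events in Groups 1, 2 and 3, plus two further control patients who would have had the outcome.

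- Both kept as events (8/36, 2/36, 2/36): chi-square 6.75, p = 0.034. Fisher's exact test p = 0.051.
- Both removed (6/34, 2/36, 2/36): chi-square 3.95, p = 0.139. Fisher's exact test p = 0.169.

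Expected event counts here are about 3 to 4 per arm, so the protocol's small-count rule would point to Fisher's test. With either test, two patients shift the result materially.

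**5. How the fever rule could bias.** All rates here are assumed. A share f of each arm has incipient infection. Risk of post-ERCP fever is 50% in these patients and 10% in the rest, with no true difference between arms. Groups 1 and 2 lose all incipient cases, so their observed risk is 10%. In Group 3, earlier antibiotics mask a share s of them, so those patients stay:

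risk in Group 3 = [(1 − f) × 0.10 + f × s × 0.50] / [(1 − f) + f × s]

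For f = 10% and s = 0.5: (0.090 + 0.025) / (0.90 + 0.05) = 0.121, a relative risk of 1.21 against Groups 1 and 2.

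| f | s = 0 | s = 0.5 | s = 1 |
|---|---|---|---|
| 5% | 1.00 | 1.10 | 1.20 |
| 10% | 1.00 | 1.21 | 1.40 |
| 15% | 1.00 | 1.32 | 1.60 |

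With equal removal in all arms there is no distortion. With unequal removal there is. Under these assumptions it works against Group 3, but other assumptions, such as open-label removal decisions that favour an arm, could give another direction.

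**The case against.** Much can fairly be said for the protocol.

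- **Timing of fever.** A reader might infer that all three removal reasons follow study treatment. For fever this is generally untrue in Groups 1 and 2. It can follow treatment only in Group 3, and only if dosing starts well ahead of ERCP. This stands. The route to bias is the asymmetry with Group 3, together with open knowledge of the arm.
- **Time of allocation.** It is not stated, and the flowchart, not reproduced in the text at hand, may give the sequence. That fever removals come after allocation is inferred from the word withdrawn and from the record-number rule. This stands as a limit.
- **Perforation and failed ERCP.** Nothing in the document suggests that antibiotics change either. Removing these patients mainly costs numbers and safety data, and it biases the comparison only if decisions differ by arm. This stands.
- **37°C against 38°C.** It is tempting to call these contradictory. The lower figure goes with the entry criterion of a temperature under 37°C, and the higher one defines the outcome after ERCP. They serve different purposes, and no contradiction is claimed.
- **The 48-hour antibiotic exclusion.** Read literally it would exclude Group 2 and, depending on timing, Group 3. The evident meaning is non-study antibiotics, so this is a matter of wording only.
- **Perforation in follow-up.** The 7-day monitoring could concern perforations found later, and adverse events are to be documented in any case. It is therefore not shown that perforation cannot be compared by arm, only that the two passages need to be reconciled.
- **The unseen analysis plan.** It may define analysis sets, so one cannot say outright that intention-to-treat is lost. But the withdrawal and exclusion rules are fixed in this protocol, and follow-up that does not take place cannot be restored later.

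**Conclusion.** The point holds as a weakness of design. Followed as written, the protocol drops patients for events after dosing (perforation, failed ERCP) or after the admission eligibility check (fever while waiting), in an open trial whose arm is readable from the record number. Removals can differ by arm, so bias can enter.

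A reader might go further and conclude that bias does enter, or that a given number of percentage points of the effect is hidden. The document does not support that: it gives no removal rates, and neither size nor direction can be derived from it. The relative risks of 1.10 to 1.60 and the shift in p-value are illustrations on assumed rates.

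What rests on the protocol's own figures is the fragility: 36 per arm, 1.8 to 6.5 expected events per arm, and 2.8 points for each patient. The power loss to 78, 76 or 73% depends on assumed losses of 5, 10 or 15%, on no replacement, and on accepting w = 0.3. That loss is modest. The possible selection matters more.

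**What to change.** 1. State the time of allocation. Carry out the final eligibility check (temperature, white cell count, prior antibiotics) immediately before allocation and first dose, and let eligibility end there.
2. Delete perforation and failed ERCP from the exclusion criteria.
3. Word the prior-antibiotic exclusion as non-study antibiotics.
4. Keep every allocated patient in follow-up and in the primary analysis as allocated. The primary outcome and day 7 are both counted from ERCP, so define an outcome window for patients without a completed ERCP.
5. Give the completed-ERCP set as a sensitivity analysis.
6. Report perforation, failed ERCP and pre-ERCP fever by arm.
7. Reconcile the withdrawal of perforated patients with the 7-day monitoring of perforation.

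None of this alters how these patients are treated. It concerns only whether they are followed and counted.

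The cost is amendment wording and the follow-up of a few patients. The downside is some dilution of the contrast from patients without a completed ERCP or given therapeutic antibiotics. It should be slight if they are few, and the sensitivity analysis will show it.
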